**Table 1. Timeline for the Design of Storytelling Intervention (ORBIT Model Phase I)**

	YR 1				YR 2				YR 3	
	Q1	Q2	Q3	Q4	Q1	Q2	Q3	Q4	Q1	Q2
Obtain IRB approval for study										
Finalize study protocols										
Begin recruitment										
Complete recruitment										
Data analysis										
Prepare R00 phase re-application										
Dissemination										
Submit IRB for R00 phase										

## **E. Potential Problems and Alternative Strategies.**

**Patient burden.** Thinking and conversing about end-of-life preferences and overall QoL may initially distress some patients and families. Some patients may decide not to participate because these issues are too difficult to deal with in the context of their illness. I have expertise from prior research experience in collecting patients' stories, and I will use strategies to conduct the conversations with a minimum of associated distress/anxiety to avoid increasing suffering. Participants' distress will be evaluated throughout the intervention, from initial audio-recording to integration of the meta-story into the EHR. A referral plan is in place for appropriate follow-up services as needed for any increased level of participant distress. If distress occurs, the participant can withdraw. To evaluate acceptability and feasibility, withdrawal data will be collected in a protocol log and discussed at research meetings; adjustments to the protocol will be completed as necessary.

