**Storytelling intervention.** As principal investigator (PI), I will conduct a storytelling intervention interview with each of the patient participants. During the interview, I will prompt the participant to share their story using probing questions such as these: tell me about your illness, tell me how your illness has affected your emotions, your relationships, your spirituality. This storytelling intervention has been field tested during my prior dissertation research (see Appendix B. Storytelling Interview Guide). I will read the prompts, concurrently take field notes of the participant's

responses, and audio-record the interview. The de-identified audio recording will be delivered via an encrypted e-mail to the transcriptionist. After the interview has been transcribed, I will review the transcripts for accuracy and create a 1- to 2-page meta-story of the participant's responses. Criteria are that the meta-story (1) is written in the first person; (2) is nonjudgmental; (3) captures the participant's voice; (4) accurately reflects the content of the interview; and (5) is nondiagnostic (not labeling). I will complete and return each meta-story to the patient participant within 48 hours. The participant and I will review the meta-story on my password-protected computer, and the participant will be encouraged to make any desired changes, facilitating co-creation of the meta-story. Once the meta-story has been approved by the participant, I will upload it to the EHR (see Appendix C. Exemplar of Meta-Story). Automated alerts, built within the EHR, will be sent to the participant's EHR-assigned nurse once the meta-story has been uploaded. To decrease complexity of the study design at the define-and-refine phase, only acute-care bedside nurses will be recruited to participate, thus acute care bedside nurses are the only providers who will receive the alert and participate in the usability testing. This workflow is depicted in Figure 3.

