#### **D. Data Collection/Analysis.**

**Specific Aim 1: Barriers and facilitators.** Two weeks after the meta-story is added to the EHR, both patient and nurse will be contacted for exit interviews to collect information about barriers and facilitators of the intervention (see Appendix D. Exit Interview Guide). The transcribed exit interviews will be entered into ATLAS.ti (a qualitative data management/analysis program). An interpretive approach will inform the understanding of the patients' and nurses' perspectives related to barriers and facilitators. Open coding, which allows codes to form patterns as they emerge from the transcripts, will be used for the thematic analysis. An inductive approach to coding, through the use of the participant's actual words, will be used for up to 3 transcripts. Once the initial codes are chosen, the transcripts will be read again through an iterative process defined as "a movement back and forth through" data coding for creating thematic analyses.54(p86) As PI, I will complete the preliminary coding for each transcript. Then the research team, which includes my primary mentor, [name], and my co-mentor, [name], will review my preliminary codes. Once the first 3 transcripts are coded, the research team will analyze the preliminary codes across the remainder of the transcripts. Throughout the entire analytical process, the codes will be refined and defined more clearly. At each of the monthly research team meetings, codes can be expanded or similar codes collapsed into larger codes as part of the iterative process for arriving at the final themes. To ensure the rigor of the data analysis, Sandelowski's criteria for trustworthiness (credibility, applicability, consistency, and neutrality) will be used.

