**Specific Aim 2: Usability testing.** Usability is defined as the relationship between humans and computers. Usability testing focuses on evaluating process measures based on four major components: user (nurse), task (utilization of meta-story by nurse), system (meta-story in EHR), and environment (inpatient nurse's station). The user-task-system-environment framework of process measures will be incorporated into the usability testing to determine barriers and facilitators from the perspective of the bedside nurse and to help determine the essential requirements for integrating the patient-centered storytelling intervention into the EHR by evaluating information flow, use of information, and system functionality. The process measures collected to determine usability will include the following: field observations of the end user (the nurse); chart review/log analysis of the nurse's use of the patient's story; time/cost analysis of the collection of the story, which includes transcribing the story, writing and co-creating the meta-story, uploading the final meta-story into the EHR, and exit interviews for both patient and nurse participants. In addition, time log analyses will be completed. These analyses will include recording the uses of the meta-story by all providers, not just the acute-care bedside nurse, to evaluate if other providers accessed the meta-story, how many times, and for what length of time the meta-story was accessed. These exploratory analyses will inform the design of future studies and how they can incorporate other types of providers as participants.

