## **F. Protection of Human Subjects**

### **Risks to Human Subjects**

#### **a. Human Subjects: Involvement, Characteristics, and Design**

A purposive sample of patient-nurse dyads will be enrolled in this study. Participants in this study are minority patients with life limiting illness (cancer, COPD, or heart failure) and their health care nurses. We expect to enroll 24 minority patients with life limiting illness and 18 nurses who are directly involved in the care of the patient. The principal investigator (PI) will enroll all participants after each of them voluntarily decide to become a participant.

**Patients.** Each patient participant will engage in two audio-recorded interviews lasting approximately 60-90 minutes. For the first interview, through a narrative analysis framework, the patients will answer open-ended questions related to their illness experiences and how their illness has impacted their emotions, relationships and spirituality. (See Appendix A-Storytelling Interview Guide). For the second interview, the patient will answer exit interview questions to capture their experience of the storytelling intervention. For the patient interviews, the location will include their private inpatient room or private conference room in the facility. If the patient is discharged prior to the second exit interview, the exit interview may take place over the telephone. (See Appendix B-Exit Interview Guide).

**Nurses.** The nurses will be interviewed once. This interview will capture exit interview data related to the storytelling intervention. The participant and nurse will be interviewed at separate times. For the nurse interview, the PI will coordinate a convenient and private place to conduct the interview which might include nurse's office or private conference in the facility. (See Appendix B- Exit Interview Guide). For the usability testing, the PI will coordinate a convenient time between at the nurse's convenience to conduct the user-task-system-environment evaluations.

The following characteristics will determine the eligibility for patient participants and nurse participants. Eligibility criteria will first be determined by the patient participant, who must be:

- (1) Over age age 18
- (2) Able to speak English
- (3) Be capable of giving informed consent
- (4) Self identify as being a racial/ethnic minority and
- (5) Have one of the following LLI: cancer, COPD, or heart failure.

Eligibility criteria for the nurses are that they be:

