- (1) Nurses will be at least age 18
- (2) Able to read, speak and write English
- (3) Confirm verbally that they were involved in the care of the patient who received the storytelling intervention.

Data collection activities for patient participants include completing the storytelling intervention via a 60-90 minute audio-recorded interview and completing an exit interview via a 60-90 minute audio-recorded interview. Data collection activities for the 12 nurse participants will include completing a 60-90 minute exit interview via an audio recorded interview. For the usability testing, data collection will include testing of the EHR interface with the bedside nurses and completion of a short questionnaire at the end of the hour session.

**Setting:** The participants will be recruited through the University of Colorado hospital.

b. **Sources of Materials**

Data for this proposed project will only be collected by the PI. Materials include audio-recordings of interviews, field notes, and correspondence (i.e., memos, emails) with research team members. A total of 60 audio-recorded interviews will be collected; 24 interviews for the storytelling intervention; 24 for the patient exit interviews, 12 for the nurse exit interviews. Safeguards for protecting anonymity of participants will include creating a master list of names with corresponding numbers assigned to participants at the time of the screening by the PI. Once assigned, the corresponding numbers will then be used to de-identify the remainder of participants' personal information and each participant's interview transcript. Only de-identified transcripts of interviews will be available for the remainder of the research team for analysis and interpretation processes.

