study. (See letters of support by [name] and [name], UC Health Research Administration).

The written consent forms will inform patients and nurses about their own participation in study activities, including randomization, participation in the intervention, and data collection and the risks and benefits of participation. The consent form for the patient participants will also include a section describing the possibility of being selected to participate in the optional qualitative exit interviews to be scheduled after the intervention. Patients and nurses will receive

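### The protocol's account of the consent forms mentions randomization and selective, optional exit interviews, but the study is observational and plans an exit interview for every patient

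*Protocol*

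**What the plan says.** **Consent.** Section F of the protocol, under Recruitment and Informed Consent, says that the written forms for patients and nurses will explain the study activities, and it lists randomization among them. The patient form will also have a section on "the possibility of being selected to participate in the optional qualitative exit interviews to be scheduled after the intervention".

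**Design and exit interview.** Section A describes the study as observational. For Specific Aim 1, section D times the exit contact with patient and nurse as "Two weeks after the meta-story is added to the EHR". Section F, under Involvement, Characteristics, and Design, says "Each patient participant will engage in two audio-recorded interviews lasting approximately 60-90 minutes". In the second of these, "the patient will answer exit interview questions to capture their experience of the storytelling intervention". Sources of Materials counts "24 for the patient exit interviews" within a total of 60 recorded interviews. Specific Aim 1 itself names patient and nurse exit interviews as a means of reaching the aim.

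**Distress.** Section E, under Patient burden, says that participants' distress will be evaluated "from initial audio-recording to integration of the meta-story into the EHR". Section C sends the alert to the participant's "EHR-assigned nurse once the meta-story has been uploaded". For Aim 2, section D plans time-log analyses that include "recording the uses of the meta-story by all providers, not just the acute-care bedside nurse".

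**The concern.** The consent paragraph fixes what patients and nurses are to be told. A form written to that description would tell them about a randomization that does not exist. It would also tell patients that they might be chosen for an exit interview, when the plan is to ask all of them. The exit interviews are the patient source that Aim 1 names, so the text that introduces them should match the plan.

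The second matter is smaller. The section E commitment to evaluate distress ends at integration into the record, which is also when the nurse is alerted and the story can be opened by clinicians. The exit interview is a dated patient contact after that point, but its stated purposes are barriers and facilitators (section D) and the patient's experience (section F). The text shown does not say that distress is asked about there.

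**Working it through.** **1. Reproduce the interview count.** The inputs are 24 patients with two interviews each and 12 nurses with one exit interview each (section F).

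- Total: 24 × 2 + 12 = 60, which matches Sources of Materials.
- Patient exit share: 24 / 60 = 40%.

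**2. Put the consent description into the same count.** If only k patients have an exit interview, the total is 24 + k + 12 = 36 + k.

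- k = 0 gives 36.
- k = 12 gives 48.
- k = 24 gives 60.

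Only k = 24 gives the stated figure, so the plan has no room for a selected subset. The range from 36 to 60 is a literal bound on what the consent wording allows. It is not a forecast of lost interviews.

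**3. Look for a selection or randomization step.** Section A states an observational design. Sections C and D describe one pathway for all patients: interview, meta-story, upload, exit interview. Nothing in them selects patients for the exit interview or randomizes anyone. The consent paragraph is alone on both points, which suggests text carried over from another design. That is an inference.

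**4. Set the distress window beside the calendar.**

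| Event | Place in the protocol | Inside the section E window? |
|---|---|---|
| Storytelling interview | Section C | Yes |
| Review and approval of the meta-story | Section C | Yes |
| Upload to the record | Section C | End of the window |
| Nurse alert, possible reading by other providers | Sections C and D | No |
| Patient exit interview, two weeks after upload | Section D | No |

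**5. Check what continues after upload.** Under Psychological, Potential Risks and Protections Against Risk give rules to stop, refer or withdraw when distress appears, and they let participants contact the investigator at any time while they take part. Potential Risks applies its stopping rule to any interview data, which includes the exit interview. The Data and Safety Monitoring Plan adds field notes on each interaction, monthly discussion of active cases, an adverse-event form with an attribution field, and a count of distress referrals. None of these ends at upload, and none sets a date for a distress check after it.

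**6. Cost of one added question.** Assume one to two minutes. The exit interview is stated as 60 to 90 minutes in most of section F and as 30 to 45 minutes under Potential Risks, Physical. The addition is therefore between 1/90 = 1.1% and 2/30 = 6.7% of its length.

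**The case against.** **On consent.** Optional may mean only the ordinary right to decline, which applies to every study activity. The paragraph breaks off in the text available, and the form itself is not shown. A reader might infer that patients were in fact misinformed. The documents do not support that, since the form may be correct. What stands is that the protocol's description is wrong: the right to decline explains optional, but it does not explain being selected, and nothing in the design explains randomization. A reader might also infer that up to 24 interviews are likely to be lost. That does not follow either. Every interview is voluntary, the 12 nurses are a goal, and patients are paid a further $50 at the exit interview.

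**On distress.** Section E is a summary sentence, and the working rules elsewhere do not stop at upload. A reader might infer that patients go unmonitored once the story is in the record, and the safeguards in step 5 contradict this. A reader might also infer that clinicians' reading of the story is a known source of distress. The protocol places the risk in discussing sensitive topics, and the patient edits and approves the story before upload. The exit interview guide is not shown and may already ask about distress. Potential Risks and Protections Against Risk are preceded by a reference to weekly assessment data under Sources of Materials, which might imply more frequent contact, but no section defines or schedules such an assessment. These objections reduce the distress point to an optional clarification.

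**On the remedy.** Potential Risks says that data collection stops if interview data reveal increased distress or an adverse event. A distress question asked early could therefore end the interview and lose that patient's Aim 1 data. This objection stands, and it determines where the question should go.

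**Conclusion.** The consent description is wrong as written on two counts, randomization and selection for the exit interview. This is more than clerical because it governs what participants are told, and it touches all 24 planned patient exit interviews. The conclusion rests on the protocol's text alone and makes no claim about the form in use.

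The distress point is secondary and optional. The stated evaluation window ends at upload for all 24 patients, and the exit contact comes two weeks later, while the reactive safeguards continue throughout. Any gain in safety from a stated check would be modest and cannot be quantified from the protocol. Neither point alters a statistical estimate, because the study is qualitative and tests no hypothesis.

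**What to change.** **Recruitment and Informed Consent (needed).** Delete randomization from the listed activities. Replace the sentence on selection with wording such as: *An exit interview is planned for every patient about two weeks after the meta-story is uploaded; patients may decline it.* Check the consent form against this wording. The cost is a correction to one paragraph.

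**Section E (optional).** Extend the distress-evaluation window through the patient exit interview. If the guide does not already ask, add one fixed spoken question on distress since the story entered the record. Put it at the end of the interview so that the stopping rule does not cut off Aim 1 data. Log positive answers on the existing adverse-event form, using its attribution field. The cost is one sentence and at most one question. The downside is one to two extra minutes (assumed) for seriously ill patients and possibly more recorded adverse events.

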## B. Description of Populations to be Enrolled.

**Setting/sample.** This study will take place at University of Colorado hospital. The participants will be minority patients with LLI and their bedside nurses. Purposeful sampling strategies will be used to recruit participants. The plan is to obtain consent from 24 patient participants equally divided (8 patients each) among three diagnostic groups: cancer, COPD, and heart failure. Data will also be collected from 12 nurse participants who provided care to the participating patients. The small sample size was chosen to be consistent with both qualitative data analysis techniques and usability data analysis techniques.

**Patient eligibility criteria.** Patients will be 18 years of age or older; able to read English; capable of giving informed consent; self-identifying as part of a racial or ethnic minority; and diagnosed with at least one LLI. The operational definition of LLI eligible for this study includes the following diagnoses: (1) metastatic solid cancer or inoperable lung cancer; (2) COPD with FEV1 values < 35% predicted or oxygen dependence; (3) New York Heart Association Class III or IV heart failure (CHF). The disease criteria were chosen to identify groups of patients with a median survival of about 2 years. These diagnoses represent 3 of the major causes of death related to LLI in the United States. Due to the nature of the qualitative design and geographical location census data, a broad group of racial/ethnic groups will be eligible to participate to allow for maximum variation sampling to collect acceptability data from a variety of groups.

[figure not shown]
**Nurse eligibility criteria.** All participating nurses will be 18 years of age or older and able to read English, and will confirm verbally that they were involved in the care of a patient who is participating in the storytelling intervention. Bedside nurses were specifically chosen as provider participants due to amount of time they interact with inpatients and the frequency with which they interface with the EHR compared to other team members. In future R01 studies of this intervention, other members of the patient's care team will be added.

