## C. Research Methods

**Patient recruitment.** I will attend University of Colorado inpatient nurse staff meetings to introduce the study, identify potential units with potential patient participants and post recruitment flyers on units. Once these units are identified, I will attend nursing rounds to identify potential patients with the assistance of the nursing care team. If a potential patient is identified by a nursing care team member, that member will provide a flyer to potential participant and obtain verbal consent. Nursing care team members will notify me of patients who provide verbal consent via secure, encrypted e-mail. I will then arrange a convenient time to meet with each patient to review the study protocols, complete screening and obtain informed consent. The consent process and the storytelling intervention interview will occur in the patient's private inpatient room. Based on my dissertation research, I anticipate that this process will take 60–90 minutes of the patient's time. For the burden of time, each patient who completes the storytelling intervention interview will receive \$50 in appreciation, plus an additional \$50 at the time of the exit interview. If the patient is discharged from the hospital, the follow-up exit interview will be collected via telephone.

**Nurse recruitment.** After a patient story is added to the EHR (see Data Collection/Analysis), I will collect from the EHR the names of the nurses who cared for the patient. These nurses will be approached for consent to participate in the study, with the goal of 12 participating nurses. For the user-centered testing, an additional 6 nurses will be recruited, for a total of 18 nurse participants. Nurses will be contacted via e-mail with a recruitment flyer. After receiving verbal consent for participation via e-mail, a convenient in-person time will be coordinated for data collection for the exit interviews. Weekly follow-up e-mails will be sent if there are difficulties recruiting the 24 nurses for data collection or the 6 nurses for user-centered testing. For the burden of time, each nurse completing the study will receive \$100 in appreciation.

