*Social.* One primary concern is the possible perception of coercion due to participant recruitment occurring in health care settings. We will attempt to avoid perception of coercion by emphasizing the voluntary nature of participation and the ability of the participants (patient or nurse) to withdraw at any time without penalty. Participants could feel pressured to participate in the proposed project. The researcher will arrange with the participants a private location with only researcher and participant present for collection of the interview. Once in this private setting, the PI will remind them that participation is voluntary and that they may withdraw from the project at any time without any penalty or prejudice.

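### Acceptability and feasibility are to be evaluated from withdrawals, but no count of patients approached or declining is planned

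*Protocol*

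**What the plan says.** Section IV.E (Patient burden) anticipates refusal for a reason that bears directly on acceptability: "Some patients may decide not to participate because these issues are too difficult to deal with in the context of their illness". Later in the same paragraph it names the data to be used: "To evaluate acceptability and feasibility, withdrawal data will be collected in a protocol log and discussed at research meetings".

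Other sections bear on the same question:

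- **Section IV.B** allows a broad range of racial and ethnic groups in order "to collect acceptability data from a variety of groups".
- **Section IV.D (Specific Aim 1)** says that two weeks after the story is uploaded "both patient and nurse will be contacted for exit interviews to collect information about barriers and facilitators of the intervention".
- **Section IV.C (Patient recruitment)** has a nursing care team member hand over a flyer and seek verbal agreement. Then: "Nursing care team members will notify me of patients who provide verbal consent via secure, encrypted e-mail". Section IV.F (Recruitment and Informed Consent) describes the same route, with screening and written consent at one later meeting with the investigator.
- **Section IV.F (Sources of Materials)** states: "Data for this proposed project will only be collected by the PI".
- **The Data and Safety Monitoring Plan** covers enrolment rate, accrual, eligibility compliance, recruitment, retention and adverse events.

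Feasibility is a declared objective of the grant and its studies (Section I).

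**The concern.** Section IV.E identifies one event, the patient who does not want this conversation, and then plans to measure a later one, the patient who joined and left. The data it names are therefore conditional on having accepted. A study with few refusals and one with many could produce identical withdrawal logs.

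The purpose of this phase is to define and refine the intervention. How often minority patients with life-limiting illness turn down an illness-story interview when offered it is basic information for the next study's recruitment plan. It is easy to note at the time and hard to recover reliably once recruitment has closed. No later analysis plan can supply it, because it depends on what is written down during recruitment.

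**Working it through.** **The plan's own figure.** Section IV.B gives 3 diagnostic groups × 8 patients = 24 patients to be consented, which agrees with its stated total. No refusal rate, withdrawal rate, number approached or acceptability threshold is given, so no effect size can be derived. The check is a tracing of the recruitment route.

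**Tracing the route for a patient identified by a nurse.**

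1. *Nurse offers the flyer.* The patient agrees or declines. Sections IV.C and IV.F provide for telling the investigator about those who agree. Nothing is planned for those who decline.
2. *Meeting with the investigator.* Screening and consent take place together. A patient may prove ineligible or may decline here. The investigator would know, but no log of either outcome is planned.
3. *After consent.* Withdrawals go into the protocol log (Section IV.E), and exit interviews are recorded (Section IV.D).

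The data named for acceptability and feasibility begin at step 3. The refusals that Section IV.E expects belong to steps 1 and 2.

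**Could another planned source fill the gap?**

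| Source | What it gives | What it lacks |
|---|---|---|
| Exit interviews (IV.D) | Views of enrolled patients and their nurses | Patients who declined |
| Enrolment rate, accrual and recruitment reports (monitoring plan) | Enrolment over time | Number approached; slow accrual looks the same with few candidates as with many refusals |
| Rounds and weekly contact with nursing teams (IV.C, IV.F) | Informal knowledge of candidates and recruitment problems | A planned count |
| Field notes and correspondence (IV.F) | Possible incidental mentions | Anything systematic |

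**Illustration, on assumed values only.** Let *u* be the share of approached patients who end up consenting. Patients approached = 24/*u*; not enrolled = 24/*u* − 24. Assume also 2 withdrawals among the 24.

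| Assumed *u* | Approached | Not enrolled | Withdrawals | Completed / approached |
|---|---|---|---|---|
| 80% | 30 | 6 | 2/24 = 8.3% | 22/30 = 73% |
| 50% | 48 | 24 | 2/24 = 8.3% | 22/48 = 46% |
| 20% | 120 | 96 | 2/24 = 8.3% | 22/120 = 18% |

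The withdrawal proportion (exact 95% interval 1.0% to 27.0%) is the same in every row. The table shows only that the named data cannot tell these situations apart. It does not predict which of them will occur.

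**The case against.** A fair defence has several parts.

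- **Section IV.E does not say at which step patients would decline.** A reader might infer that the protocol expects refusals specifically at the nurse's approach. It does not say so. The approach is simply the first decision point for a nurse-identified patient, and the consent meeting is another. This stands, and the point is worded to cover both steps.
- **The protocol is silent; it does not rule out a record.** A reader might infer that refusals are lost beyond recovery. The documents do not support that. The investigator attends rounds, speaks weekly with nursing teams and keeps field notes, so some refusals may become known. What stands against the plan is narrower: none of these channels is set up to give a count.
- **The withdrawal sentence follows the remark that a distressed participant may leave, and is not called the sole evidence.** True. But the sentence states its purpose as evaluating acceptability and feasibility, and the qualitative sources share the same limit to enrolled people.
- **Declining a recorded research interview is not the same as finding the intervention unacceptable.** This stands. Refusals also reflect whom nurses choose to approach, fatigue, recording and interview length. It limits interpretation, but it does not make the count useless.
- **The aims concern barriers, facilitators and usability in a purposive sample, with no uptake target.** This also stands, and it sets the weight of the point.

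**Conclusion.** The point holds as a cheap improvement. For evaluating acceptability and feasibility, Section IV.E names only data that arise after a patient has accepted, while expecting refusals that no section plans to count. Accrual monitoring and informal contact with the wards do not supply the missing denominator.

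Its size cannot be stated, because the documents give no uptake figure. A reader might go further and conclude that the acceptability result will be biased or that the study's aims are compromised. Neither follows: the protocol sets no acceptability rate or threshold that could be biased, and the thematic and usability analyses of Aims 1 and 2 concern enrolled participants.

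The conclusion rests on two readings: that withdrawal means leaving after enrolment, and that notifying the investigator of patients who agree does not extend to those who decline.

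**What to change.** Amend Sections IV.C (Patient recruitment), IV.E (Patient burden) and IV.F (Recruitment and Informed Consent), with IRB approval, to add two records kept by the investigator:

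1. **Approach count.** At the weekly rounds already planned, the investigator asks nursing teams how many patients were given the flyer and notes agreed or declined, by diagnosis group. No names or record numbers are taken. A reason is noted only if the patient volunteered one. Nurses do not ask, given the protocol's own caution: "One primary concern is the possible perception of coercion due to participant recruitment occurring in health care settings".
2. **Consent-meeting log.** The investigator notes ineligibility and refusal separately.

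Because the investigator keeps both, the statement in Sources of Materials that data collection is the investigator's alone can stand.

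Report the flow descriptively beside the withdrawal log: approached, agreed, eligible, consented, story approved, exit interview done. Count separately any patient who contacts the investigator from a posted flyer. State that refusals also reflect nurse selection, fatigue and other reasons, so they are not a pure measure of acceptability.

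**Cost.** An IRB amendment, minor recall effort for ward nurses, and possibly a less favourable feasibility picture. No new staff or patient procedure is needed. Two limits remain: counts recalled weekly may be incomplete, and most refusals will carry no reason. The record can help separate few candidates from many refusals, but it cannot establish that the topic was the cause.
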